4.28. Pilot study

There will be a 3-month pilot phase, during which the team will hire and train study staff and test standard operating procedures, data collection forms, and data management. Many practical arrangements and standard operating procedures (SOPs) will be adopted from earlier ABCD and SANTE -trials, also testing various aspects of azithromycin impacts on children and currently being carried out in Mali, with the same Malian co-PI as in LAKANA trial.

Mortality data from the first two 3-month intervals, from the villages that will be enrolled in the first week of trial activities, will be treated as pilot data and not included in the main database for trial analysis.

4.29. Quality assurance and control

Internal quality assurance is implemented using standard operating procedures (SOPs) and weekly internal monitoring. The team in Mali will employ 1-3 quality assurance officers, who will regularly work with the staff on quality assurance procedures. For external monitoring, the team will contract a clinical research organization that will complete a pre-site trial assessment, quarterly monitoring visits during the trial implementation, and data collection closure visit. Additionally, Tampere University staff members will conduct bi-annual internal monitoring visits to the study sites.

If requested, the investigators will make study documents (e.g., consent forms, drug distribution forms, case report forms) and pertinent hospital or clinic records readily available for inspection by the site auditors for confirmation of the study data if the study site is selected for auditing by the Comité D'Ethique de la FMPOS (Faculte de Medicine, de Pharmacie et D'Odonto-Stomatologie, Universite des Sciences, des Techniques et des Technologies de Bamako).

4.30. Originally planned time schedule

(not updated after version 1.0)

In total, the project will take 4 years and 2 months. The detailed time schedule is below.

November - December, 2019

Finalising research plan

Approval of the plan by appropriate institutional

- review boards (IRB)
- Developing SOPs and planning practical arrangements
- Developing data entry and management system

January – March 2020

Finalising data entry and management system
Staff recruitment and training
Obtaining study drugs

April 2020 – March 2021

First study visits at all study villages

April 2021 – December 2021

Completion of 4 MDA rounds in all villages

January 2022

Interim analysis. Dropping placebo if justified

January 2022 – September 2022

Completion of all main study follow-up visits

October 2022 – December 2022

Data cleaning and analysis

January 2023 – December 2023

Write-up of main study results (mortality,

- Write-up of main study results (mortality, morbidity, and growth outcomes)
- Local results dissemination on main outcomes
- Completion of AMR follow-up visits and analyses, international and local results
- Dissemination on AMR outcomes
- Continued feasibility analyses
- Roll-out of azithromycin MDA program, if indicated

Figure 10 shows a graphic illustration of trial schedule. Planned interim analysis is marked in transparent red color. To shorten the trial period by six months, the last enrolled villages will be followed up only for 7 MDA rounds (30% of villages) or 6 MDA rounds (20% of villages).

5. Statistical considerations and data analysis

5.01. Specific hypotheses

The main study hypotheses in terms of mortality effect are the following:

1. Biannual azithromycin MDA to 1-11 month (29-364 days) old infants reduces their mortality
2. Quarterly azithromycin MDA to 1-11 month (29-364 days) old infants reduces their mortality
3. Quarterly azithromycin MDA has a bigger mortality effect than biannual MDA

The study hypotheses in terms of other health effects are the following:

4. Quarterly azithromycin MDA to 1-11 month (29-364 days) old infants reduces their 14-day period prevalence of fever with respiratory symptoms (ARI), fever without respiratory symptoms (malaria), and diarrhea
 - a. Separately, there is a similar hypothesis on the effect of biannual azi MDA
5. Quarterly azithromycin MDA to 1-11 month (29-364 days) old infants reduces their health facility visits for ARI, malaria, diarrhea, and other conditions
 - a. Separately, there is a similar hypothesis on the effect of biannual azi MDA
6. Quarterly azithromycin MDA to 1-11 month (29-364 days) old infants improves their length gain, and nutritional status (MUAC, WHZ)?
 - a. Separately, there is a similar hypothesis on the effect of biannual azi MDA

The study hypotheses in terms of intervention health effects on AMR are the following:

7. Quarterly azithromycin MDA to 1-11 month (29-364 days) old infants does not cause a sustained increase in the prevalence of phenotypic azithromycin resistance among *S. pneumoniae* or *E. coli* strains isolated from their nasopharyngeal secretions or stools.
 - a. Measured at 12 months after the intervention has stopped
 - b. Separately, there is a similar hypothesis on the effect of biannual azi MDA
8. Quarterly azithromycin MDA to 1-11 month (29-364 days) old infants does not increase the prevalence of azithromycin resistance among *S. pneumoniae* or *E. coli* strains isolated from 49–59-month-old children, who live in the same Malian communities but have not received azithromycin MDA?
 - a. Measured when the intervention has lasted for 12–18 months
 - b. Separately, there is a similar hypothesis on the effect of biannual azi MDA
9. Quarterly azithromycin MDA to 1-11 month (29-364 days) old infants does not cause a sustained increase in the prevalence of azithromycin resistance genes in their intestinal microbiota.
 - a. Measured when the intervention has lasted for 12–18 months
 - b. Separately, there is a similar hypothesis on the effect of biannual azi MDA
10. Quarterly azithromycin MDA to 1-11 month (29-364 days) old infants does not increase carriage of azithromycin resistance bacteria in treated infants 1 year after

their treatment has stopped, who live in a village where MDA intervention has also ceased.

- a. Measured after the intervention for individual child has stopped for 1 year
- b. Separately, there is a similar hypothesis on the effect of biannual azi MDA

11. Quarterly azithromycin MDA to 1-11 month (29-364 days) old infants does not increase carriage of azithromycin resistance bacteria in treated infants 1 year after their treatment has stopped, who live in a village where MDA intervention has continued.

- a. Measured after the intervention for individual child has stopped for 1 year
- b. Separately, there is a similar hypothesis on the effect of biannual azi MDA.

The study hypotheses in terms of azithromycin mechanism of action are the following:

12. Azithromycin MDA reduces malaria prevalence and parasite density, and improves mean blood hemoglobin concentration among 4–11-month-old infants, within 14 days of the MDA
 - a. For these analyses, the two azithromycin can be combined
13. Azithromycin MDA reduces general inflammation (CRP) among 4–11-month-old infants, within 14 days of the MDA
 - a. For these analyses, the two azithromycin can be combined
14. Azithromycin MDA reduces intestinal inflammation (fecal neopterin, myeloperoxidase, and alpha-1-antitrypsin concentrations) among 4–11-month-old infants, within 14 days of the MDA
 - a. For these analyses, the two azithromycin can be combined

There is no predefined hypothesis about the impact of biannual or quarterly azithromycin MDA to 1–11-month-old infants on mortality among 12–59-month-old children living in the same communities, but we will measure group-level differences on this as exploratory analysis.

There are also no predefined hypotheses about the feasibility, acceptability, or equity of the azithromycin MDA intervention.

5.02. Analytical approach

The study team will express mortality in the three groups as number of deaths per 1000 person-years at risk (deaths/PYR) and AMR as the proportion of *E. coli* or *S. pneumoniae* isolates that have reduced susceptibility (R or I category) towards azithromycin. For pairwise comparisons between any of the two groups, the team will calculate incidence rate ratio and its 95% confidence interval (CI) for mortality and risk ratio and its 95% CI for AMR prevalence at 12 and 24 months after the onset of the azithromycin MDA intervention.

As an exploratory analysis, the team will also assess mortality (deaths / 1000 years at risk) among children who were 12–59-month-old at the time of the previous study drug administration in their village of residence. There is no predefined hypothesis for this

analysis, but it can provide information about possible herd protection generated through targeted azithromycin MDA.

Mixed-effect Poisson regression model will be used to estimate the intervention effects on mortality, with random intercepts for the clusters. For twins, no adjustment for interdependence will be made, i.e. we plan to analyse the data assuming independence between infants from the same mother. This is because our previous methodological research has demonstrated that analytic models that assume independence are robust in situations where cluster size is small and only a few of the analysable units are clustered (such as 1-2% twin rate, Xu et al., 2014). As per the closed-testing method for controlling multiplicity arising from multiple group comparisons, global null hypothesis of mortality in all three groups being the same will be tested at 5% significance level. Pairwise null hypothesis can be rejected only if the global null hypothesis has been rejected. Pairwise incidence rate ratio and corresponding 95% confidence intervals will be estimated.

For the main analysis, we will analyse the mortality data of infants/children who receive azithromycin/placebo at the age of 1-11 months (29-364 days) at the beginning of each 3-month period. Some of the person-time and deaths may occur at age 12-14 months during the 3-month periods. This is consistent with the study aim to assess the effect of MDA giving at the age of 1-11 months (29-364 days). As a secondary analysis, we will use the Lexis expansion approach to partition the follow-up time and deaths into intervals of 1-5, 6-11, and 12-14 months of age (and also 1-11 and 12-14 months) and cross-classified with intervals defined according to the 3-month periods. This allows for more precise estimation of age-specific intervention effects and more precise adjustment for the time period effects.

For AMR, the team will calculate the risk differences (and their two-sided 95% CIs) for AMR prevalence in azi-quarterly and azi-biannual groups as compared to the control group, separately. If the entire 95% CI of the risk difference of a MDA regime is below a predefined non-inferiority margin of 0.1 (meaning less than 10%-point absolute increase in AMR prevalence), the sample findings will be considered supportive of the hypothesis of no clinically significant increase in AMR prevalence for that regime.

For morbidity analyses, we will calculate 14-day period prevalence of fever with respiratory symptoms (ARI), fever without respiratory symptoms (malaria), and diarrhea in the three intervention arms and do a three-group comparison using likelihood ratio tests. The latter will be obtained from mixed-effects logistic regression models, which accounts for the clustering of observations. If the test shows a statistically significant difference ($p < 0.05$) between the three groups, we will proceed into three pair-wise comparisons, providing relative risks (RR) and their 95% CIs. Hypothesis testing in these pairwise comparisons will be done with likelihood ratio test obtained from mixed-effects logistic regression models. If the p -value is < 0.05 , the results will be considered supportive of the trial hypothesis.

For growth analysis, we will calculate anthropometric indices LAZ (length for age Z-score), WAZ (weight for age Z-score), WLZ (weight for length Z-score), and MUAC-Z (mid upper arm Z-score) for each participant as described in chapter 4.10. We will then calculate mean (SD) group values for each variable. In analyzing differences between groups, controlling for multiplicity will be conducted as per the closed-testing procedure,

by testing a global null hypothesis at 5% significance level. If the global null hypothesis is rejected ($p<0.05$), three pairwise comparisons will be carried out. The differences between the three groups and their 95% CIs will be obtained from mixed-effects regression models, that account for the clustering of observations. The global p-value will also be obtained from these models.

For mechanism of action analyses, we will calculate the prevalence of malaria parasitemia as well as mean plasma CRP, blood hemoglobin and other biomarker concentration before and at two weeks after the MDA. We will then test a global hypothesis about differences between the groups using mixed-effects models, which account for clustering, for continuous variables and proportions, respectively with different, suitable link functions. If the global test shows a statistically significant difference ($p<0.05$) between the three groups, we will proceed into three pair-wise comparisons, providing the difference (95% CI) in means or proportions. If the p-value obtained from mixed-effects models is <0.05 , the results will be considered supportive of the trial hypothesis.

All children will be analysed in the group into which they were initially randomized, i.e. on an intention-to-treat basis.

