We will test the first three of the above-described hypotheses (about malaria elimination and reduction of general or intestinal inflammation) from the first group of children, i.e., 4–11-month-old infants living in communities receiving their 4th MDA. From these infants, a study nurse will collect a heel-prick blood sample and a flocculated rectal swab before they have received any MDA. They will collect another heel prick blood sample and a stool sample (or rectal swab if stool collection fails) two weeks after the 4th round of MDA has been conducted in their communities. From the collected blood, the nurse will measure hemoglobin and CRP concentration with an on-site reader and store blood on a filter paper for later malaria diagnostics with DNA-amplification. From the stool sample, a laboratory technician will determine calprotectin and alpha-1-antitrypsin concentrations with commercially available ELISA tests. Additional stool and urine samples will be collected and stored for later analyses (on hypotheses 5-7). In the analysis phase, we will compare prevalence of malaria parasitemia, mean blood hemoglobin and CRP concentration and mean fecal neopterin, myeloperoxidase, and alpha-1-antitrypsin concentration in the three study arms, both before and after the first MDA treatment.

From the second and third group of children (12–14-month-olds who have received 3-4 doses of MDA and 6–8-month-olds who have received 2-3 doses of MDA) we will test hypotheses 2-4, i.e., those about broader general and intestinal inflammation and immune function and development. These infants will be invited to a health facility or a central location in a village - after the MDA visit to their household. At the clinic, a study nurse will receive a home collected stool sample or take a rectal swab if stool collection has failed. S/he will also draw a 5 ml blood sample and collect a 10 ml

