urine sample, which will be delivered to a nearby study laboratory by a motorcycle messenger. A laboratory technician will measure Hb, separate plasma and white blood cells, aliquot plasma, urine and stool, and store the samples at -80°C freezer. Approximately once a month, the stored samples will be shipped to a central laboratory at CVD-Mali in Bamako, where another laboratory technician will perform the immunological and inflammatory assays. In the analysis phase, we will compare mean plasma concentrations of vaccine antibodies and selected cytokines, thymic output, the ratio of naïve to memory CD4 and CD8 sub-populations in the three study arms. For the azi-biannual group, we will perform an additional exploratory analysis to assess the impact of timing of the azithromycin dose (given at 1-2 and 6-8 months of age vs at 3-5 and 9-11 months of age).

For hypothesis on microbial clearance and reduction of inflammation, we expect to see the largest effect in infants who have not received azithromycin earlier. We also expect that age of the child may be an effect modifier. Hence, we primarily focus on one time-point (fourth MDA) and a wide age-bracket (4–11-month-old infants). The youngest infants (less than 4 months old) will be excluded for logistical reasons as they will not be invited to sample collection for AMR analyses. Since we want to be able to track individual level changes in test variables, we will collect and analyse samples before and after the MDA. The chosen blood analyses can be completed a battery-operated on-site reader from a small volume taken with a heel-prick – and hence we will not need to take any venous samples from these children.

For the hypotheses on immune function and development, we expect to see the largest effect among infants who have received repeated MDA doses. Therefore, we will choose children at a time when there have been at least 4 rounds of MDA in their home villages. At this point, most or all the 12–14-month-old children have received 3-4 MDA doses and 6–8-month-old children have received 2-3 doses. For the immune function and maturity analyses, we will need a larger blood volume and hence we will take it by a venous puncture, at a study clinic after MDA. Since we are interested in a cumulative effect of multiple MDA doses and only want to do group level comparisons, there is no need for paired sample collection.

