The age groups have been selected in a way that there will be no more than one venous blood sample per child during the study. From the 6-8-month of children, we will primarily assess immune development and vaccine responses to tetanus and rotaviral vaccines (given before the age of 6 months). From the 12-14-month of children, we will assess immune development and vaccine response to measles vaccine (given usually between 9 and 12 months of age). From both age-groups, we will also assess malaria prevalence by a DNA amplification test. Immune development and infection are best studied among over-6-month-old children, since by this age infants will have lost most of their passive maternal immunity and will be increasingly susceptible for infection, inflammation, dysbiosis, and EED.

Figure 7 summarises analyses planned to be completed in the first phase.

Study question	Biological specimen	Laboratory analysis	Child age	Level of analysis	Timing of lab sample vs MDA	# of given MDA doses	# of children
Malaria clearance	Blood (dried)	P. falciparum DNA amplification	4-11 mo	Individual	Paired (before and 14 d after)	1	1000
Consequence of malaria clearance	Blood (fresh)	Hemoglobin concentration	4-11 mo	Individual	Paired (before and 14 d after)	1	1000
Reduction of systemic inflammation	Blood (fresh)	CRP concentration	4-11 mo	Individual	Paired (before and 14 d after)	1	1000
Reduction of intestinal inflammation	Stool	Calprotectin concentration	4-11 mo	Individual	Paired (before and 14 d after)	1	1000

Figure 8 summarises biological samples planned to be stored from the study participants (in addition to those, stored in the AMR part of the study). These samples will be used address hypotheses 5-7 of the mechanistic studies as well as for any additional hypotheses formulated during the trial. If all samples were collected and aliquoted as planned, there would be a total of 51,800 stored vials, i.e., these samples will fill one -80°C freezer.

Biological specimen	Child age	MDA or study visit	Timing of lab sample vs MDA	# of given MDA doses	Storage media	Estimated # of aliquots	Volume / aliquot	Storage temperature	# of children
Blood	4-11 mo	4	Before	1-3	Filter paper	2	50 ul	-80°	1000
Stool	4-11 mo	4	Before	1-3	Cryovial	4	1.5 g	-80°	1000
Urine	4-11 mo	4	Before	1-3	Cryovial	3	1.5 ml	-80°	1000
Blood	4-11 mo	4	14 d after	1-3	Filter paper	2	50 ul	-80°	1000
Stool	4-11 mo	4	14 d after	1-3	Cryovial	4	1.5 g	-80°	1000
Urine	4-11 mo	4	14 d after	1-3	Cryovial	3	1.5 ml	-80°	1000

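### The mechanism sub-study takes paired samples around MDA 4, but the stated analysis compares arms at each time point and so does not target the 14-day effect named in hypotheses 12-14

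*Combined protocol and SAP*

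**What the plan says.** **Design.** Section 4.17 samples infants aged 4-11 months before and two weeks after the fourth MDA in their village. The reason given for two samples is that "we want to be able to track individual level changes in test variables". For the immune-function analyses the same section says that pairing is not needed, because only group-level comparisons are wanted. Figure 7 gives the level of analysis as individual, the timing as "Paired (before and 14 d after", and 1,000 children per analysis.

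**Hypotheses.** In section 5.01, hypotheses 12-14 each concern an effect "within 14 days of the MDA", and each allows the two azithromycin arms to be combined.

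**Analysis.** Section 5.02 computes parasitaemia prevalence, mean CRP, and "blood hemoglobin and other biomarker concentration before and at two weeks after the MDA". It then says "We will then test a global hypothesis about differences between the groups using mixed-effects models, which account for clustering". If the global test is significant, pairwise comparisons follow, "providing the difference (95% CI) in means or proportions". A p-value below 0.05 counts as support for the trial hypothesis. Section 4.17 likewise describes a comparison of the three arms "both before and after the first MDA treatment".

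**The concern.** The design is justified by within-infant change, but the analysis as worded compares arms at each time point. Two things follow.

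First, the test may answer a different question from the hypothesis. If earlier rounds have already shifted the marker, the arms differ before round 4 is given, and a day-14 difference can arise without any effect of round 4. Since 5.02 does not name the time point of the global test, even a pre-dose difference could, read literally, count as support.

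Second, how the pairs are used decides both what is estimated and how precisely. That choice would remain open when the data are analysed.

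**Working it through.** **1. Reproduce the stated detectable effect.** Section 5.04 gives 0.25-0.30 at 80% power and two-sided 5%, with 333-450 infants per arm and a design effect (DE) of 1.6-2. For one measurement per child and equal arms:

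detectable effect = (1.960 + 0.842) x sqrt(DE x 2/n)

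- n = 333: 0.274 (DE 1.6), 0.307 (DE 2)
- n = 450: 0.236 (DE 1.6), 0.264 (DE 2)

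The range 0.24-0.31 matches the stated one. The stated power therefore rests on a single measurement per child and takes no credit for pairing.

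**2. Earlier exposure.** Rounds are three months apart and treatment starts at 29 days. An infant aged 4 months at round 4 was about 1 month old at round 3. One aged 11 months was about 8, 5 and 2 months old at rounds 3, 2 and 1. That gives one to three earlier eligible rounds, as Figure 8 lists (1-3 doses). The pre-MDA-4 sample is thus post-randomisation and, in the azithromycin arms, may already reflect treatment.

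**3. What each contrast estimates.** Let earlier rounds shift the marker by d (the same at both samples), let round 4 add t, and let r be the pre/post correlation.

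- Day-14 contrast: d + t
- Difference in change: t
- Day-14 contrast adjusted for the pre-MDA-4 value: t + d(1 - r)

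Illustrative values in SD units:

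| d | t | day 14 | change | adjusted, r = 0.3 / 0.5 / 0.7 |
|---|---|---|---|---|
| 0 | -0.30 | -0.30 | -0.30 | -0.30 / -0.30 / -0.30 |
| -0.15 | -0.15 | -0.30 | -0.15 | -0.255 / -0.225 / -0.195 |
| -0.30 | 0 | -0.30 | 0 | -0.21 / -0.15 / -0.09 |

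A simulation with 333 independent children per arm agreed with these values to within about 0.01. Three quite different truths give the same day-14 contrast. Adjustment removes only part of the carry-over.

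**4. Precision.** The documents give no r, so a range is assumed. Relative to the day-14 contrast, variance is multiplied by 2(1 - r) for the difference in change and by 1 - r^2 for baseline adjustment. With 333 per arm and the DE held at 2, the day-14 contrast has a detectable effect of 0.307 and 78.2% power at 0.30 SD. The alternatives are:

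| r | change: factor, detectable, power at 0.30 | adjusted: factor, detectable, power at 0.30 |
|---|---|---|
| 0.3 | 1.40, 0.363, 63.9% | 0.91, 0.293, 81.9% |
| 0.5 | 1.00, 0.307, 78.2% | 0.75, 0.266, 88.5% |
| 0.7 | 0.60, 0.238, 94.2% | 0.51, 0.219, 97.0% |

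These apply to continuous markers and do not size the change for parasitaemia.

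**5. Azi-biannual exposure at round 4.** Section 4.06 gives this arm azithromycin at January-June visits and placebo at July-December visits. The season of round 4 in the Kita villages is not stated. Section 4.08 places the tertiary mechanistic samples in the rainy season. Where round 4 falls in July-December, this arm has no azithromycin dose at that round, yet 5.01 allows it to be combined with azi-quarterly.

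**6. Conflicting timing.** The group definitions in 4.17 and Figure 8 place the pairs around the fourth MDA. The sampling paragraph of 4.17 describes the first sample as taken before any MDA and refers to the first MDA treatment, and Figure 7 lists one dose.

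**The case against.** The best defence is that 5.02 lists no model terms for these outcomes, so a pre-dose or child-level term is unstated rather than excluded, and that Figure 7 labels the analyses individual and paired. This stands in part. A reader might infer that the infant's own pre-dose value never enters the test and that the pairing is lost; the documents do not establish that. They show that the comparisons they do spell out are between arms at each time, and that the use of the pairs is not specified.

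It can also be said that the day-14 contrast is a sound randomised comparison. It is, for the regimen received up to that point. And if the first-MDA wording in 4.17 described the actual sampling, the pre-dose sample would be untreated and the day-14 contrast would estimate that dose's effect. The mismatch therefore depends on the fourth-MDA design, which the group definitions and Figure 8 support.

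Another tempting inference is that adjusting for the pre-MDA-4 value would both recover precision and isolate the round-4 dose. It does the first only; step 3 shows what remains.

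Nor do the documents support a claim of chance imbalance based on the 60 Kita villages alone. Section 4.08 adds a similar number of villages nearer Bamako, and an arm difference before MDA 4 mixes chance with real earlier effects.

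**Conclusion.** The point holds as a mismatch between hypothesis and stated analysis. Sections 4.17 and 5.02 describe between-arm comparisons at each time, name no term that uses the pairs, and leave the time point of the global test open. Given one to three earlier rounds, the day-14 contrast estimates the cumulative regimen effect, not the 14-day effect of that round. If earlier rounds had produced a -0.30 SD shift and round 4 added nothing, the plan could still read the result as support for hypotheses 12-14.

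How large the carry-over is cannot be known from the documents; the SD values above are illustrations. The same is true of precision: without r, no definite loss can be claimed, and the contrast that targets round 4 is less precise than the day-14 contrast when r is below 0.5. The difference in change isolates round 4 only if the arms would otherwise have changed in parallel over the 14 days.

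Only the secondary mechanism outcomes are affected. The mortality analysis is not.

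**What to change.** In section 5.02:

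- **Test of hypotheses 12-14.** Use a joint pre/post mixed model with arm, time, arm-by-time, and random intercepts for village and child (logit link for parasitaemia). Take the arm-by-time term as the effect of the round-4 treatment, and state the parallel-change assumption and its scale. Infants with one missing sample stay in the model. Consider a village-by-time random effect as well, because a village intercept alone cancels from the change and would leave village-shared change out of the standard error.
- **Day-14 contrast.** Keep it unadjusted, labelled as the cumulative-regimen effect. A version adjusted for the pre-MDA-4 value may be reported as a sensitivity analysis, with a note that this value is post-randomisation and that the contrast does not fully isolate the round-4 dose.
- **Azi-biannual arm.** For hypotheses 12-14, count these infants as exposed to azithromycin at round 4, and combine them with azi-quarterly, only where the visit fell in January-June. Compare them with control infants seen in the same half-year.

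In section 4.17, reconcile the before-any-MDA and first-MDA wording and the single dose in Figure 7 with the fourth-MDA design.

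The cost is a short paragraph in 5.02 and a text correction in 4.17, with no new samples. The downsides are less precision than the day-14 contrast if r is below 0.5, and a smaller exposed group wherever azi-biannual visits fell in July-December.
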